One delivery option that has not been explored in-depth is providing PGx testing through the community pharmacy. As pharmacists have expertise about drugs and regularly interact with both patients and providers, they occupy a unique position in the health care delivery team and may be ideally suited to provide PGx testing. Patients often rely on their community pharmacist not only to dispense medications, but as a source of medical information and for other health services (e.g., vaccinations)²⁷. Some commercial laboratories have begun to establish partnerships with community pharmacies to offer PGx testing, but to our knowledge, no studies have been conducted about pharmacists' preparedness, interest, utility, or patient experiences with PGx testing in this setting.

To address patient needs and maximize outcomes of PGx testing, it has been proposed to deliver PGx testing as part of MTM.^{28,29} MTM services have transitioned from primarily patient education and counseling to systematic and coordinated processes for comprehensive medication

management.³⁰ MTM is currently being utilized in community pharmacies and ambulatory care settings as a standard of care to address adherence, side effects, duplication of therapies, and prevention of possible drug interactions. Though practices can vary,³¹ MTM services typically include five core elements: 1) medication therapy review, 2) personal medication record, 3) medication-related action plan (MAP), 4) intervention and/or referral, and 5) documentation and follow-up.³² Typically conducted by a pharmacist, MTM can be helpful for physicians and patients to improve medication adherence. MTM has been shown to be effective for some patient populations in reaching clinical goals, increasing compliance with recommended lab monitoring, reducing re-hospitalizations and inappropriate prescribing and risk of ADRs, and improving adherence.^{20,33-39} For a range of clinical goals, MTM has also been demonstrated to be cost-effective.^{35,40,41}

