PGx Testing Only Arm. Participants in this arm will receive only PGx testing. Prior to testing, the pharmacist will review PGx testing with the patient, including the purpose of testing, description of test, test limitations, and anticipated outcomes, using any of the toolkit resources provided as desired/needed. Upon patient consent, a buccal sample will be collected and sent for PGx testing. When testing is completed, the pharmacist will review the PGx results and the participant's medication history to determine if drug or dosage adjustments should be considered based on the test results. Results may be provided to the patient using the PGx wallet card or patient test report provided in the toolkit. If the patient is taking another medication impacted by the same PGx gene and there is strong evidence regarding dose adjustment/drug selection based on genotype, recommendations for additional drug or dosing changes will be made. The pharmacist will contact all patients to discuss their result, even for patients with a "normal" test report, and if any changes to their medications are indicated. The pharmacist will also contact the participant's provider if changes are indicated. In the event that MTM is clinically indicated for a patient who undergoes PGx testing in this arm, pharmacists should provide the service and we will exclude these patients from the study.

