and can read and write in English, and have a new or existing prescription (<1 year active) for a drug listed in Table 1 to be eligible to participate. Each pharmacy will identify existing patients eligible for testing through a query of their database for active prescriptions for the selected drugs. If more than 30 patients in a pharmacy are identified by the database search, we will ask pharmacists to contact patients with the newest prescriptions. Patients will be contacted by phone or in-person by the pharmacist to introduce the study. Interested patients will be asked to visit the pharmacy to learn more about testing, sign the consent form requested by the testing laboratory, and provide a DNA sample (buccal swab). Patients who have had PGx testing for one of the genes in Table 1 or had an MTM within the past 12 months will be ineligible. All women and minorities who meet the study inclusion criteria will be eligible to participate in the study. Based on our power calculations, we estimate that we would need to enroll 18 patients per cluster (360 total).

Patients who consent to testing based on their pharmacist's recommendation will be asked to provide a buccal swab for DNA extraction. Patient samples will be sent for testing to Pathway Genomics laboratory. Testing will be provided at no cost for participants. As the Pathway Genomics' clinical tests are currently available to any clinician, only the consent required by the testing lab will be required of the patient.

Patients in the control arms will be identified by each participating pharmacy; two controls will be identified per each participant in the PGx arms (2:1) and matched on drug, age and gender. Time on treatment, medication changes (dose/drug selection), and refill history (adherence) data will be collected along with demographic data and compared to patients in the PGx testing arms. Based on their pharmacy records, patients who have undergone MTM or PGx testing outside of the study will be excluded from the control arm.

Risk/Benefit Assessment. If patients decide to have pharmacogenetic testing, a buccal swab sample is required. There are no known risks to a buccal swab sample. The sample, or DNA extracted from the sample, will be sent to the laboratory and stored only for the time necessary laboratory regulations.

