- **[Baseline & Follow-up]** Several secondary clinical outcomes will be measured to assess overall impact of PGx testing during the follow-up survey including information-seeking about side effects of new drugs and medication adherence. To assess medication adherence, we will use a combination of survey tools and refill data from the pharmacies. Participants will be asked to complete the validated Beliefs about Medicines Questionnaire (BMQ)¹⁰⁴ and Voils medication adherence scale (<https://sites.duke.edu/corrinevoils/versions-of-scale/>). Higher concerns and lower necessity measured by the BMQ have been associated with poorer medication adherence.^{105,107} Although the MMA scale is generally the more accepted tool for self-reported adherence, the BMQ scores can be used as a covariate to determine reasons for non-adherence (e.g., poor satisfaction). In addition, we will assess the psychological impact of testing using the Multidimensional Impact of Cancer Risk Assessment (MICRA) questionnaire.¹⁰⁸ The total score on anxiety and distress subscales range 0 to 105 with a higher score indicating more distress. No studies have defined a cut-off value for high distress; therefore, we will follow the approach by Bjornslett et al¹⁰⁹, and define high distress as a MICRA score above the mean +1 standard deviation.

Pharmacist Patient Log. We will ask pharmacists to keep track of their interactions with each patient to enable analysis of feasibility of delivery of PGx testing in a pharmacy setting and compare responses between pharmacy and patient surveys (see Appendix 7). In particular, we will ask pharmacists to document reason for each interaction with a patient, time spent addressing interaction, whether by phone or in-person, the test result, time spent following up with patient's provider, whether any drug or dosing adjustments were made based on the test result, and refill data. Pharmacy adherence data will extend 6 months after test results are communicated. Two measures of adherence based on data from the pharmacy will be generated: 1) the proportion of days covered¹¹⁰⁻¹¹² (PDC; # of days with drug on-hand]/[# of days in the specified time interval] (x 100)]; and 2) medication possession ratio (MPR; # of days of

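### Matched controls are screened for prior MTM and PGx testing by a wider, undated rule than participants, and MTM is handled differently in each of the three groups

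*Combined protocol and SAP*

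**What the plan says.** Part II, Patient Study Population, contains both rules. The participant rule, which sets grounds for ineligibility, begins: "Patients who have had PGx testing for one of the genes in Table 1 or had an MTM within the past 12 months will be". The control rule is worded differently: "Based on their pharmacy records, patients who have undergone MTM or PGx testing outside of the study will be excluded from the control arm".

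The same section says that "two controls will be identified per each participant in the PGx arms (2:1) and matched on drug, age and gender". It then lists the control data to be set against those of the tested arms: "Time on treatment, medication changes (dose/drug selection), and refill history (adherence) data will be collected along with demographic data and compared to patients in".

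For a PGx-only patient in whom MTM becomes clinically indicated, the PGx Testing Only Arm section says that "pharmacists should provide the service and we will exclude these patients from the study". The MTM + PGx arm has no counterpart, since MTM is its assigned service.

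The Pharmacist Patient Log section in Part III sets the refill window: "Pharmacy adherence data will extend 6 months after test results are communicated". Controls receive no test results, and the plan gives them no equivalent date.

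**The concern.** A matched comparison is interpretable when both sides were drawn by the same rule. Here the same history admits a patient on one side and bars the patient on the other. The history in question is also unlikely to be neutral. The background text states that "MTM is currently being utilized in community pharmacies and ambulatory care settings as a standard of care" and ties it to adherence problems, side effects, duplicate therapies and interactions. It adds that insurers and employers offer it to people with many comorbid conditions, and that it can lead to recommended regimen changes. Patients with an MTM history may therefore differ on the outcomes for which controls are collected.

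Both randomised arms are tested, so the controls are the only concurrent untested group. Aim 2 places medication adherence in the trial's primary goal, and the Data Analysis section hypothesises that awareness of genetic risk improves adherence. Any estimate of what testing adds to medication changes or refill adherence rests on this comparison.

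**Working it through.** **Step 1. The rules side by side**

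| | Participants | Controls |
|---|---|---|
| Prior MTM | Barred if within the past 12 months | Barred if recorded at any time, outside the study |
| Prior PGx testing | Barred for Table 1 genes; unclear whether the 12 months applies here too | Barred for any PGx testing outside the study |
| Reference date | Entry | None given |
| MTM during follow-up | PGx-only: removed if clinically indicated. MTM + PGx: no removal | Not stated |

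**Step 2. Test cases**

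- Last MTM 18 months ago: eligible as a participant, barred as a control.
- Earlier PGx test of a gene outside Table 1: eligible as a participant, barred as a control.
- MTM in month 3 after the results date: a PGx-only patient is removed if MTM was indicated; an MTM + PGx patient stays. A control stays if records are checked at selection, but is dropped if they are checked when the 6-month data are extracted. The text allows either.

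Matching on drug, age and gender does not balance MTM history.

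**Step 3. Size, on assumed inputs**

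The documents give no MTM frequency and no medication-change rate. Let m be the share of participants in a stratum that is removed from controls only, and d that stratum's excess medication-change rate. If r is the rate in everyone else, participants show (1 − m)r + m(r + d) and controls show r. With no true effect of testing, the difference is m × d.

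- Low: 0.02 × 0.05 = 0.1 percentage points.
- Middle: 0.10 × 0.20 = 2.0 points.
- High: 0.20 × 0.30 = 6.0 points.

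The same formula covers the follow-up reading. If 10% of controls received MTM within 6 months, with a change in 40% of them and 10% of the rest, all controls would show 0.90 × 0.10 + 0.10 × 0.40 = 13%, but the retained controls 10%: a gap of 3 points. With 5% receiving MTM and 30% changing, the gap is 0.05 × 0.20 = 1 point; with 15% and 50%, it is 0.15 × 0.40 = 6 points. These figures need the open-ended reading and a usual-care comparator. In the PGx-only arm the bias would be partly offset by that arm's own removals.

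**Step 4. Scale**

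The plan's enrolment is 20 pharmacies × 18 = 360 participants, which agrees with its stated total. Two controls each gives 720. Assume a base change rate of 10% to 25%, two-sided 5% significance and 80% power, ignoring clustering and matching. The detectable difference is then 6.0 to 8.2 points.

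With no true effect, the rejection rate under a bias b follows from x = b / √[p(1 − p)(1/360 + 1/720)], where p is the pooled rate. At a 10% base and b = 2 points, p = (360 × 0.12 + 720 × 0.10)/1,080 = 0.1067, the standard error is 0.0199 and x is about 1.00, so the false-positive rate is 17%. At a 25% base it is 11%. A 1-point bias gives about 6.5% to 8%.

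**The case against.** The strongest reply is that the consequence is limited and unproven. The randomised arms are compared without the controls, and the primary outcome is comprehension of a test result, which controls do not have. Participants' qualifying prescriptions are under one year active, so an MTM more than 12 months earlier would generally predate them, which weakens its link to outcomes on that drug. Part III restricts clinical outcomes to medications impacted by PGx, so MTM changes to other drugs would not count. The sponsor may also have wanted controls who had received neither service. All of this stands. It limits the size, but it does not explain why the two sides use different rules.

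Three stronger readings are tempting, and the documents do not support them.

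- A reader might infer that controls are removed during follow-up. The sentence sits in the paragraph on identifying controls and can equally mean history at selection. The supportable point is that the timing is unspecified.
- A reader might infer that only controls lose patients over MTM. The PGx-only arm also loses them after enrolment, so one-sided loss during follow-up could arise mainly for MTM + PGx against controls. The look-back mismatch concerns both PGx arms.
- A reader might infer that the rule raises control adherence. MTM is directed at adherence problems, but the background also credits it with improving adherence. Removing its recipients could move control adherence either way.

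**Conclusion.** The exclusion rules differ on their face, for MTM in look-back and for PGx testing in gene scope. The missing control index date leaves MTM and outside testing during follow-up without a defined treatment. Together with the PGx-only removal, this means MTM is handled differently in all three groups. The control comparison of medication changes, time on treatment and refill adherence may therefore partly reflect selection.

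The size cannot be derived from the documents. The range of 0.1 to 6.0 points for medication changes rests wholly on assumed values, and the effect is small unless prior MTM is common and strongly related to outcome. For medication changes, the likelier direction is to overstate what testing adds; for adherence, the direction is open. The control rule does not touch the primary comprehension endpoint. What the PGx-only removal does to the randomised comparison is a separate question, not assessed here. The point is worth acting on because the change costs little and the controls are the only untested group.

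**What to change.** In Part II, Patient Study Population:

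1. Give each control an index date matched to its participant, for example the date the participant's results are communicated, when the 6-month refill window starts.
2. Apply the participants' exclusions to controls over the same look-back: no MTM in the 12 months before, and the same prior-PGx rule for Table 1 genes. State whether the 12 months applies to PGx testing as well. Decide eligibility only on records up to the index date.
3. For the control comparison, set one analysis rule in all groups for MTM or outside PGx testing after the index date: retain the patient, record the date, and report a sensitivity analysis that censors at the event. Include the patients whom the PGx Testing Only Arm section now removes; keeping later-MTM controls while still dropping those patients would create a new imbalance. MTM delivered as the assigned intervention in the MTM + PGx arm is not an event, and session 1, which precedes the results, does not count in the look-back.

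This concerns the analysis only and does not change who is given MTM.

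The cost is a few sentences, a date condition in the record query and one extra analysis. The downside is that some controls will have received MTM, so the main contrast is with usual care; the sensitivity analysis covers the contrast without MTM.

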The integration of PGx testing into the community pharmacy setting will be assessed primarily through surveys of patients and pharmacists. In addition, we will conduct semi-structured interviews with a subset of pharmacists to gather more in-depth understanding of their experiences, perceived barriers, and likelihood to continue to offer PGx testing. The measures to be assessed are described below; clinical outcome measures will be collected about the medications impacted by PGx only.

Patient Surveys (Aim 2b) The baseline survey will collect demographic data, prior knowledge about PGx, self-reported co-medications, time on treatment for PGx-related drug(s), and medication adherence (see Table 2; Appendix 5). The follow-up survey will gather data on 1) satisfaction with the testing experience in a pharmacy setting, including use/provision of patient materials from Aim 1; 2) perceived value of testing; and 3) comprehension of test result. Additional measures include medication-taking behaviors and information-sharing. The follow-up survey will be administered approximately one month after the PGx results are communicated since many of the medications are prescribed in 90-day allotments. Key survey questions are further described below; data on age, gender, co-medications, and time on treatment for PGx-related drug(s) will also be collected for controls.

- [Baseline] Literacy. We will screen for health literacy using the validated single question: “How confident are you filling out forms by yourself?” Compared to the gold standard literacy tools REALM or S-TOFHLA, this single question accurately predicts inadequate health literacy⁹⁹ and is more feasible to administer.
- [Follow-up] Comprehension of Results. Our primary outcome will be comprehension of test results based on gist recall of the phenotype.¹⁰⁰ Specifically, the outcome of interest is the patient’s recognition of the presence or absence of a variant gene. Due to the complexity of genotypes and presumed patient unfamiliarity with gene nomenclature, we do not believe it reasonable to expect patients to recall their genotype. Therefore, we will instead ask patients to circle their specific metabolizer status (e.g., rapid, extensive, intermediate, poor, or inconclusive). For the genes *SLCO1B1* and *VKORC1*, we will ask patients to indicate their test

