Survey Data Analysis. Analysis of data collected from surveys will be conducted using a software package such as STATA. We will calculate frequency data and statistical associations for the respondent characteristics. Both univariate and multivariate analyses will be conducted for hypotheses (see below). Because the trial uses a cluster design, the analysis will use logistic mixed effects regressions by including treatments as the fixed effect of interest and clusters as random effect. We will first test if the random effect is significant or not. If not, then we will use regular logistic regression to perform the analysis; if significant, we will continue using mixed effect logistic model. In either case, odds ratios and 95% confidence intervals will be generated to assess strength of associations between treatments and outcomes. A secondary analysis will be performed in which the comprehension outcome is not collapsed into “correctly identifying the presence of any variant versus no variants”, but will include correctly indicating the result for each gene (e.g., slow/fast metabolism vs. average). In this case, a logistic random effects model will also be applied with pharmacist and patient as random effects. If a sufficient number of patients are enrolled per drug, a stratified data analysis by drug will be performed to detect any differences regarding comprehension, adherence, or satisfaction. In addition, the impact of time to treatment will be assessed on patient satisfaction and adherence.

- We hypothesize that patients will have a higher level of comprehension of test results from the MTM plus PGx testing than those receiving testing offered as a stand-alone service.
- We hypothesize that patients overall will be satisfied with PGx testing provided through the community pharmacy and likely to have testing again in this setting
- We hypothesize that patients will find PGx testing beneficial, particularly those who have experienced adverse responses or a poor drug outcome in the past, are taking multiple medications, and are older.
- We hypothesize that patients' increased awareness about their genetic risk to adverse responses will result in improved adherence through assurance about the effectiveness and/or safety of their medications.
- We hypothesize that the additional time required to deliver PGx testing as part of an MTM session may present a barrier to providing PGx testing through this approach.

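### The refill-adherence comparison with matched controls has no start date or active-prescription rule for controls, so current users may be compared with patients who have stopped or are long-term users

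*Combined protocol and SAP*

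**What the plan says.** Refill adherence is described in Part III, Pharmacist Patient Log. The only period given is "Pharmacy adherence data will extend 6 months after test results are communicated". Two measures are derived. PDC divides days with drug on hand by "days in the specified time interval". The medication possession ratio (MPR) is defined over the refill interval.

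Controls are described in Part II, Patient Study Population: "two controls will be identified per each participant in the PGx arms (2:1) and matched on drug, age and gender". Their "refill history (adherence) data will be collected along with demographic data and compared to patients in the PGx testing arms". The only stated control exclusion is MTM or PGx testing outside the study.

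Tested patients enter by a narrower route. Pharmacies "identify existing patients eligible for testing through a query of their database for active prescriptions". The prescription must have been active for less than a year, and where the search finds more than 30 patients the newest prescriptions come first. The prescriber must sign the requisition, and the patient then visits, gives a swab and waits 7 to 10 days for the laboratory.

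Time on treatment is collected for controls. The Data Analysis section adds that "the impact of time to treatment will be assessed on patient satisfaction and adherence". Neither statement sets a window or a matching rule.

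**The concern.** PDC depends heavily on whether the patient is still taking the drug when counting starts, and on how long treatment has already lasted. Tested patients are normally still on a fairly recent prescription when their result is communicated. A control who meets the stated matching rule may have stopped months earlier, or may be a settled long-term user. The first kind of control makes testing look helpful; the second can make it look harmful.

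The comparison bears on a stated hypothesis, that patients' "increased awareness about their genetic risk to adverse responses will result in improved adherence". Both randomised arms are tested, so the controls are the only concurrent untested group with refill data. The Data Analysis section names no model for tested patients against controls, so nothing there settles the window either.

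**Working it through.** **The plan's own figures.** The plan gives no sample size, effect size or standard deviation for this comparison, so there is no result to reproduce. Enrolment is 20 pharmacies × 18 = 360 tested patients, and 2:1 matching implies 2 × 360 = 720 controls.

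**Assumptions (none is in the documents).** No true effect of testing; a constant stopping rate L of 2%, 5% or 10% per month; 95% of days covered while on the drug; a six-month window that opens on the communication date.

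**Tested patients**, on the drug at day 0: PDC = 0.95 × (1 − e^(−6L)) / (6L).

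**Reading (a).** Controls take the matched date but need only a first fill at some time in the previous 12 months. The share still on the drug is f = (1 − e^(−12L)) / (12L), and control PDC = f × tested PDC.

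**Reading (b).** Controls are measured over the six months before their records are pulled and are still active at the pull. Control PDC = 95%.

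| | L = 2% | L = 5% | L = 10% |
|---|---|---|---|
| Tested PDC | 89.5% | 82.1% | 71.4% |
| f | 0.889 | 0.752 | 0.582 |
| (a) control PDC | 79.6% | 61.7% | 41.6% |
| (a) tested − control, all controls affected | +9.9 | +20.4 | +29.8 |
| (b) tested − control, all controls affected | −5.5 | −12.9 | −23.6 |
| (a) 20% of controls affected | +2.0 | +4.1 | +6.0 |
| (b) 20% of controls affected | −1.1 | −2.6 | −4.7 |
| 95% half-width, 360 v 720 | 2.3 | 3.3 | 4.0 |

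Differences and half-widths are in percentage points. The 20% rows are one fifth of the rows for all controls. The half-width is 1.96 × SD × √(1/360 + 1/720), with the SD of tested PDC under the model (17.9, 25.9 and 31.8 points) used for both groups. It ignores clustering and matching. At 20% affected, the bias exceeds the half-width at L = 5% and 10% under (a), and only at L = 10% under (b).

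**Sensitivity to the assumptions.** With 85% of days covered and stopping of 1% to 8% per month, reading (a) with all controls affected gives +4.8 to +24.1 points.

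**Does aligning the date and requiring current use remove the bias?** Only if the stopping rate is constant over treatment. Suppose instead that stopping is 4% per month for the first three months of treatment and 2% after, with tested patients at month 1 and controls at month 9, all on the drug at day 0.

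- Tested PDC = (0.95/6) × [(1 − e^(−0.08))/0.04 + e^(−0.08) × (1 − e^(−0.08))/0.02] = 86.6%.
- Control PDC = 89.5%.
- Difference = −2.9 points.

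With 10% and then 5% per month the values are 75.7% and 82.1%, a difference of −6.4 points. Time on treatment therefore matters in its own right.

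All of these calculations concern PDC. MPR was not modelled.

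**The case against.** The strongest reply is that this is a clarification to one secondary, non-randomised comparison, and that a sensible analyst would use the matched patient's date and pick controls who are on the drug. Matching on drug, and recording time on treatment and refill history, does point that way. The appendices, including the patient log form, are not among the documents reviewed and could hold a rule. The largest figures need every control to be affected, and the stopping rates are assumed. All of this stands, and it is why the size is best stated for a minority of controls. It does not close the gap: the matching rule as written admits controls who have stopped or are long-term users.

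Some stronger readings are tempting but not supported:

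- A reader might infer that the trial's adherence results as a whole are compromised. They are not. Both randomised arms have a communication date, and the primary comprehension outcome does not involve controls.
- A reader might infer that controls are the only evidence on the adherence hypothesis. Self-reported adherence is taken at baseline and again at follow-up ("The follow-up survey will be administered approximately one month after the PGx results are communicated"), so within-patient change is also available.
- A reader might take communication day as the documented opening of the window. The text says how far the data run; opening on that day is the natural reading, but it is not stated.
- A reader might conclude that aligned dates bring the bias to zero. The plan does not match on time on treatment, and tested patients are volunteers whose prescriber agreed to testing.

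**Conclusion.** The concern holds for the comparison of refill adherence between tested patients and 2:1 controls. The only stated period depends on an event that controls never have. The matching rule does not ask for an active prescription, the under-one-year limit or similar time on treatment. PDC can be biased in either direction. Under assumed stopping of 2% to 10% per month and no true effect, the bias is about 1 to 6 points if 20% of controls are affected, and 5.5 to 29.8 points if all are. These figures illustrate a range and do not estimate the bias in this trial. A rule in the unseen appendices would reduce or remove the gap.

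**What to change.** In Patient Study Population and Pharmacist Patient Log:

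1. Give each control its matched patient's communication date as day 0.
2. Apply one active-prescription rule at day 0 to both groups, including the limit of less than one year active.
3. Compute PDC over the same six months from day 0 in both groups.
4. Keep MPR on its stated refill-interval definition, using refills from that same period.
5. Match on time on treatment in bands, or adjust for it; it is already collected.

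In Data Analysis, name the comparison of tested patients with controls, and account for the matched set and the pharmacy.

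The cost is a few sentences, with no extra patients, visits or consent. Pharmacies can match on site and send coded day counts. Controls must be pulled after the matched date is known. Some tested patients will have fewer than two controls, and some will fail the day-0 rule and leave this comparison, so a fallback is needed, such as one control or a wider band. Volunteer selection remains and should be reported as a limitation.
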